Official Title: An Open-Label Application of the NSS-Bridge Device for Post-Cesarean Pain

ClinicalTrials.gov ID (NCT number): NCT03830307

Document Date: 2/1/2019

Project Title: Feasibility and Tolerability of the Use of NSS-Bridge Device for Post-Cesarean Pain**Management****Introduction**

The current opioid epidemic has led to a renewed interest in exploring non-pharmacological techniques to treat post-operative pain. An increasing number of patients are suffering from the adverse effects of opioid use following surgery, including post-operative nausea and vomiting, respiratory depression, immunosuppression, constipation, and most recently, addiction. In the United States, over \$600 billion is spent every year on opioid addiction, including \$79 billion related to opioid addiction following surgery. Despite many initiatives to decrease the use of opiates in the preoperative setting, opioids continue to be regularly prescribed before, during and after surgery. Although the risk of opioid addiction following surgery is recognized, the percentage of patients becoming addicted to opioids following surgery is not well understood. To date, there has been virtually no agreement regarding the duration and dosage that qualify for opioid dependence following surgery, nor that a clear estimation of the factors such as biological, psychosocial and socioeconomic that increase the risk of using opioids for extended periods of time after surgery. Therefore, in order to combat this growing health crisis at the ground level, it is incumbent upon the medical community to explore alternative methods of pain control to treat the surgical population in order to reduce the incidence of post-operative opioid addiction.

Project Aims/Goals

Percutaneous Nerve Field Stimulation (PNFS) is one of these recognized methods that ongoing research has shown to be effective as a complementary method of pain management. While PNFS is not a novel concept, clinical indications of auricular field stimulation have been limited in the past due to requirement of bulky, stationary and non-disposable stimulators and electrodes. These technological

limitations made it difficult to establish the real clinical potential of auricular stimulation for the perioperative management of pain in surgical patients, despite the demonstration that auriculotherapy has been shown to relieve pain in the postoperative setting.

The NSS-2 BRIDGE (Appendix 1) is a battery operated and disposable percutaneous auricular nerve field stimulator (Innovative Health Solutions, Versailles, IN, USA), that was recently cleared by the FDA and assigned a Class II Risk Designation; a class which includes surgical drapes, pumps and power wheelchairs. The indication for the NSS-2 BRIDGE is for the treatment of clinical symptoms related to opioid consumption and opioid withdrawal. These symptoms include abdominal pain, anxiety and post-operative nausea and vomiting; conditions which are also present following Cesarean-Section surgery. The use of the NSS-2 BRIDGE device has been demonstrated to provide significant analgesia in patients with abdominal pain syndrome, and clinical trials are ongoing to assess the benefit of this approach for post-operative pain management. As compared to the present use of opioids for perioperative pain management, the use of a complementary, non-pharmacologic approach offers the advantage of analgesia without the associated side effects. This is especially true in the post Cesarean Section population, in that many of these women want to breast feed and because of this are very motivated to not use opioids and other analgesics, allowing us to explore the additional benefits of non-pharmacological complementary pain management techniques.

Mechanism of action of the Auricular Percutaneous Electrical Nerve Field

The NSS-2 BRIDGE device allows for stimulation to branches of Cranial Nerves V, VII, IX and X, and the occipital nerves, identified by transillumination. Such a stimulation is transmitted to the central nervous and especially the limbic system, which is known to be a key component of the central nervous system response to stress, anxiety and the pain pathway. The nucleus involved by the stimulation include the amygdala (structure involved in the response to fear and anxiety), the thalamus (structure

involved in the management of visceral and somatic pain, addiction), the nucleus of tractus solitarius (structure involved in the control blood pressure) etc.... The stimulation of these nucleus produces a decrease in the transmission of pain impulses from visceral and/or somatic structures to supraspinal areas, a reduction in anxiety and control of blood pressure and associated changes of the sympathetic and parasympathetic nervous system.

The primary end point will be the frequency of patients who experience an excellent tolerability along with a decrease of at least 20% in pain score. Also pain score and opioid consumption will be compared to data obtained 5 consecutive who underwent a C-section the month before.

Specific Aims

Specific Aims:

1. Tolerability and feasibility of applying the device following Cesarean Section
2. Look at the trend of opioid consumption and pain in five post- Cesarean section women wearing device, compared to five historical consecutive controls of women who underwent cesarean section in January 2019

Study Design

The proposed pilot study will be conducted as a single-center prospective open-label trial at the University of Pittsburgh Medical Center (UPMC) Magee-Womens Hospital. The data collected during this period will be compared to historical controls who have had elective C-Sections in the period of January, 2019. Institutional review board approval will be obtained before eligible patients are recruited and consented. Trial will be registered at www.clinicaltrials.gov before beginning recruitment.

Recruitment

Potential subjects will be recruited in the Magee Womens Hospital obstetrical unit when they arrive for elective Cesarean Section surgery. The Principal Investigator, [name] [name], will already have access to these patients as their primary OB Anesthesiologist. Patients will be asked for their interest in pursuing a research study that involves wearing a percutaneous, auricular field stimulator for five days as a supplementary method of post-operative pain control after their Cesarean-Section. Patients who agree to participate in the trial will sign an IRB approved Informed Consent Form.

Inclusion Criteria:

Over 18 years of age

Elective Cesarean-Section Surgery

Exclusion Criteria:

History of active depression, anxiety or catastrophizing

Active alcoholism or drug abuse

Severe chronic pain condition that requires daily preoperative opioid dependence

History of hemophilia

Patients with cardiac pacemakers

Patients with psoriasis vulgaris diagnosis

Data Collection and Outcome Measures

The primary purpose of this pilot study is to demonstrate feasibility/acceptability of the NSS-2 Bridge device applied after a C-section. If the acceptability is confirmed, the C-section model will be included in an RFA NIH request (RFA-NS-19-018: HEAL Initiative: Clinical Devices to Treat Pain (UH3 Clinical Trial Optional) DEADLINE IS MARCH 8, 2019) for proposal related to the use of devices for reduction of opioid use. In this pilot, no changes will be made in the other analgesia/postpartum care. Potential subjects will

be recruited in the Magee-Womens Hospital obstetrical unit when they arrive for cesarean delivery. Patients will be asked if they are interested in using the NSS-2 Bridge system as a way to control pain after the C-section. They will offer to review a video explaining the mechanism of action of the NSS-2 Bridge system. Subject will be informed of the purpose of this pilot evaluation and if they agree to participate in the trial, they will sign an IRB approved Informed Consent Form.

Once patient has given and signed informed consent to participate in the study, demographic information and medical history will be collected from each participant on the day of the C-section. Data will be de-indemnified and kept in a lock cabinet. The NSS-2 BRIDGE device will be applied to one ear by trained research staff in the immediate post-operative setting. The patient will be informed at the time of consent and after the implantation of the device that they can have the device removed any time after its application.

As per standard of care, at 12, 24, 48, 72, 96 and 120 hours post-operatively will be collected pain score at rest and movement, total opioid consumption, as well as the device tolerability. Additionally as per other pain pilot IRB approved projects, we shall also collect common medical information including time to bowel movement, PONV, time to oral intake (liquid and regular diet), time to hospital discharge, intensive care unit (ICU) admission, readmission to the hospital, readmission due to pain related issues, quality of recovery after cesarean delivery, overall patient satisfaction, and patient satisfaction related to pain management. When the patient is discharged from the hospital, they will be asked to complete a patient satisfaction survey. For patients discharged with the device attached, removal instructions will be given to patient to remove and dispose of the device at 120 hours.

Standard opioid conversion table will be used to convert the oral and IV narcotic utilized by the patients to IV morphine equivalent doses (MED) for analysis purposes.

Overall patient satisfaction and satisfaction of pain management during hospitalization will be measured by a numerical rating scale with 0- worst satisfaction and 10 being the best satisfaction. The patient satisfaction test will be administered by a member of the research team.

No statistical analysis will be performed. The primary end point will be the frequency of patients who experience an excellent tolerability along with a decrease of at least 20% in pain score. Also pain score and opioid consumption will be compared to data obtained 5 consecutive who underwent a C-section the month before

Pre-and-Post Metric Evaluation

The use of a non-pharmacological NSS-2 BRIDGE has the possibility of providing analgesia to post-surgical patients and reducing the number of opioids required following Cesarean-Section surgery. This will significantly impact patient outcomes, as patients will experience fewer opioid-related side effects (such as respiratory depression, post-operative nausea and vomiting, constipation and delirium, as well as transfer of opioids to the breast milk). This will also impact clinicians caring for post-operative patients, as there is the real potential they will have fewer conditions to monitor and treat as the patient recovers from surgery. The projected number of patients served by this project will initially be five (5) enrolled participants at Magee-Womens Hospital however, the data collected from this trial will serve countless patients and the community at large as physicians strive to move away from opioid use following surgery. Data collected from this pilot study will support a future proposal to the National Institute of Health (NIH) to fund a full-scale, randomized, placebo-controlled trial using the NSS-2 BRIDGE device.

Perhaps most importantly, the investigative use of the non-invasive NSS-2 BRIDGE device has the ability to significantly increase patient satisfaction in individuals who are opioid naïve or adverse to taking opioids as a method of pain control. Being able to offer the post-partum patients at Magee

Womens Hospital of UPMC such an alternative represents a great opportunity to increase patient satisfaction, outcomes and compliance as many patients increasingly fear the use of opioids. The NSS-2 BRIDGE will remain effective on the participant for five days, and will have lasting effects even after discharge from the hospital, which is a time when many patients turn to opioids to control pain. The way the efficacy of this device will be measured will be by comparing total perioperative opioid consumption between study participants (n=5) historical controls who have had C-Sections at Magee Womens hospital in January 2019. Other outcome measures include the incidence of respiratory depression, PONV, constipation and length of stay between the study group and historical control group.

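### The protocol does not apply the device patients' exclusion criteria to the historical controls and does not fix where the consecutive series of controls starts

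*Protocol*

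**What the plan says.** The protocol describes the historical controls in five places.

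- The paragraph just before Specific Aims, and again Data Collection and Outcome Measures: pain score and opioid consumption are "compared to data obtained 5 consecutive who underwent a C-section the month before".
- Specific Aims, Aim 2: the device patients are "compared to five historical consecutive controls of women who underwent cesarean section in January 2019".
- Study Design: the comparison is with "historical controls who have had elective C-Sections in the period of January, 2019".
- Pre-and-Post Metric Evaluation: the controls are women who had a cesarean at the same hospital in January 2019.

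The inclusion and exclusion lists stand after the Recruitment text. Inclusion requires elective cesarean. Three exclusions bear on pain and opioid use: "History of active depression, anxiety or catastrophizing", "Active alcoholism or drug abuse" and "Severe chronic pain condition that requires daily preoperative opioid dependence". The protocol speaks of eligibility once, in Study Design, where ethics approval must be in place "before eligible patients are recruited and consented".

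Pre-and-Post Metric Evaluation says that efficacy will be measured by comparing total perioperative opioid consumption with these controls. It adds respiratory depression, nausea and vomiting, constipation and length of stay to the same comparison. Elsewhere the protocol gives feasibility and acceptability as the primary purpose, frames Aim 2 as looking at a trend, and plans no statistical analysis.

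**The concern.** A comparison with historical controls is only as good as the rule that selects them. Here the stated rule is consecutive women with a cesarean in a given month. Followed literally, it admits a woman with daily opioid dependence, active substance abuse or active depression or anxiety, while the same woman could not enter the device group. The protocol itself treats these features as relevant to the outcome: its introduction lists psychosocial factors among those that raise the risk of prolonged opioid use after surgery, and its section on mechanism links anxiety to the pain pathway.

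The start of the series matters for a separate reason. The document is dated 2/1/2019, so the January surgeries had probably been done and many control outcomes may already have been on record. Five consecutive women with no stated starting point leaves a choice of run that could be made after outcomes are visible.

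Since no analysis is planned that could adjust for a mismatch, the control definition is the main protection the comparison has. The data are meant to support an application for a full-scale trial.

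**Working it through.** **Step 1: the five descriptions side by side.**

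| Place in protocol | Consecutive | Elective | Exclusions mentioned | Start of series |
|---|---|---|---|---|
| Before Specific Aims | yes | no | no | no |
| Aim 2 | yes | no | no | no |
| Study Design | no | yes | no | no |
| Data Collection and Outcome Measures | yes | no | no | no |
| Pre-and-Post Metric Evaluation | no | no | no | no |

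Elective appears in 1 of 5, the exclusions in 0 of 5, and a starting point in 0 of 5. The first and fourth rows are the same sentence repeated, so there are four distinct wordings. No single one gives number, order, elective status and eligibility together.

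**Step 2: is the missing word elective a real difference?** Probably not. Aim 2 calls the device patients "five post- Cesarean section women wearing device", also without the word, and Data Collection and Outcome Measures drops it for them too, although inclusion requires it. The omission looks like shorthand, and Study Design supplies the limit. No comparable sentence supplies the exclusions.

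**Step 3: how much one control can move the result.** The protocol gives no doses, no variability and no share of ineligible women, so there is no figure of its own to reproduce. From n = 5 alone, one control weighs 1/5 = 20%. Assume that exactly one control is ineligible, that she uses k times the dose of the other four, and that the device has no effect:

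- shift of the control mean = 0.2 × (k − 1)
- apparent reduction = 1 − 1/(1 + 0.2 × (k − 1))

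| k (assumed) | Shift of control mean | Apparent reduction |
|---|---|---|
| 0.5 | −10% | 1 − 1/0.9 = −11.1% |
| 1.5 | 10% | 1 − 1/1.1 = 9.1% |
| 2 | 20% | 1 − 1/1.2 = 16.7% |
| 3 | 40% | 1 − 1/1.4 = 28.6% |

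With no ineligible control, both are 0.

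**Step 4: how likely is at least one ineligible control?** If a share p of unscreened women would meet an exclusion (assumed, women independent), the chance is 1 − (1 − p)^5: 0.23 at p = 5%, 0.41 at 10%, 0.67 at 20% and 0.83 at 30%.

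**Step 5: chance error for scale.** With five per group, equal means and an assumed coefficient of variation CV, the standard error of the difference as a share of the mean is CV × √(2/5): 31.6% for CV = 50% and 63.2% for CV = 100%. Of the shifts in Step 3, only the 40% at k = 3 exceeds one standard error, and only towards the low end of that CV range.

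**The case against.** The strongest reply is that this rests on silence. No sentence says that the controls are unscreened, the criteria stand under their own headings without being confined to device patients, and an analysis plan not shown could hold the operational rules. Part of this stands: the protocol does not state a different rule for controls. But it does state a selection rule, consecutive women in a given month, and that rule taken literally yields a less comparable group. Who the controls are is also normally settled in the protocol, and this one undertakes to settle it.

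Two stronger readings are tempting, and the document supports neither.

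- A reader might infer that four descriptions admit non-elective controls and so contradict Study Design. They are general phrases compatible with the specific one, and the device patients receive the same shorthand.
- A reader might infer that the bias must favour the device, because opioid-dependent women are kept out of one group only. That is plausible, but no figure in the document establishes it, and the assumed range includes a shift the other way.

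It is also fair to say that the consequence is modest. The primary endpoint, tolerability together with a pain decrease of at least 20%, is counted in the device patients and is not defined against the controls. Chance error with five per group is usually larger than the illustrated bias. And screening the controls leaves another difference in place: device patients volunteer for a supplementary pain method, while controls are picked from charts.

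**Conclusion.** The point holds as a gap in the control definition. The protocol neither applies the device patients' exclusions to the historical controls nor says where the consecutive series starts, so screened patients may be compared with unscreened ones on opioid use and pain. The uneven use of the word elective is a wording matter that Study Design already resolves.

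Size and direction are unknown. The only figure that needs no assumption beyond n = 5 is the 20% weight of each control. The illustrated range of −11% to 29% depends on the assumed k and on exactly one ineligible control. The weight is low: the comparison is descriptive, in a feasibility pilot with five women per group. It is not nil, because the protocol itself calls this comparison the way efficacy is measured and nothing planned later would correct a mismatch. This is an inexpensive improvement to the plan; it does not threaten the primary purpose.

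**What to change.** Use one control definition in all five places: the first five consecutive elective cesareans at the hospital from a stated date in January 2019, in women who meet the trial's own inclusion and exclusion criteria as far as the chart shows. Fix the date before any control outcome is read. Bring the four descriptions that omit elective into line with Study Design.

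The cost is one sentence and a few more charts. If a share p of charts fails the check (assumed), the average number read to reach five controls is 5/(1 − p): 5.0 at 0%, 5.6 at 10%, 6.3 at 20% and 6.7 at 25%. Treatment, visits and sample size do not change.

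The change improves comparability, not precision. Catastrophizing may not be charted, so some mismatch will remain. The difference between volunteers and chart-selected controls also remains, and the report should acknowledge it.

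### The historical reference is limited to five women without a stated reason, and the protocol's descriptions of that reference disagree on its number and on elective status

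*Protocol*

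**What the plan says.** The protocol describes the reference group in four ways.

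- **Specific Aims, Aim 2:** the trend in opioid use and pain among the device group is to be "compared to five historical consecutive controls of women who underwent cesarean section in January 2019". The number is five and elective status is not mentioned.
- **Endpoint sentence** (just before Specific Aims, and again under Data Collection and Outcome Measures): "Also pain score and opioid consumption will be compared to data obtained 5 consecutive who underwent a C-section the month before". The number is five and elective status is not mentioned.
- **Study Design:** the data will be "compared to historical controls who have had elective C-Sections in the period of January, 2019". These are elective cases, with no number.
- **Pre-and-Post Metric Evaluation:** efficacy is to be measured by "comparing total perioperative opioid consumption between study participants (n=5) historical controls who have had C-Sections at Magee Womens hospital in January 2019". The n=5 belongs to the participants. The controls have no number and are not called elective.

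The device group is five throughout: "The projected number of patients served by this project will initially be five (5) enrolled participants at Magee-Womens Hospital". The inclusion and exclusion criteria are written for participants and are not stated to apply to controls. Demographics and medical history are planned for participants only. The protocol states that no statistical analysis will be done, and names feasibility and acceptability as the primary purpose.

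**The concern.** The size of the device group and the size of the reference group are separate decisions. Each device woman must be approached, consented and fitted with a device. The controls had their surgery in January 2019, and the protocol is dated 2/1/2019, so their data can only come from existing records. Keeping the controls at five to mirror the device group brings no visible benefit, and the protocol offers none.

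This matters because the protocol asks more of the comparison than a glance at a trend: the efficacy statement rests on it, and the pilot data are meant to support a grant proposal for a full-scale trial. With no test or interval planned, readers will see the raw contrast, and one heavy or light opioid user among five controls can move it a good deal. The sections also disagree on how many controls there are and whether all are elective, so two abstractors could build different reference groups from the same protocol.

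**Working it through.** **Inputs.** Device group 5 and controls 5 (Aim 2). The protocol gives no SD, effect size, alpha or power, so there is no stated calculation to reproduce. Results are in SD units, assuming equal SDs in the two groups. The number of January 2019 elective cesareans is not given; 20 to 100 is an assumed range.

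**Step 1: share of the variance due to controls.** With m controls, Var(difference in means) = SD² × (1/5 + 1/m). At m = 5 this is 0.400 SD², and the controls' share is (1/5)/(1/5 + 1/5) = 50%. Each control carries 1/5 = 20% of the reference mean. If the control SD is r times the device SD, the share is r²/(1 + r²): 36% at r = 0.75 and 69% at r = 1.5.

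**Step 2: gain from more controls.** SE = √(1/5 + 1/m) in SD units. The half-width is t(0.975; 5 + m − 2) × SE.

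| Controls m | Variance (SD²) | SE (SD) | SE reduction | Pooled-t 95% half-width (SD) |
|---|---|---|---|---|
| 5 | 0.400 | 0.632 | – | 1.46 |
| 10 | 0.300 | 0.548 | 13% | 1.18 |
| 20 | 0.250 | 0.500 | 21% | 1.03 |
| 50 | 0.220 | 0.469 | 26% | 0.94 |
| 100 | 0.210 | 0.458 | 28% | 0.91 |
| no limit | 0.200 | 0.447 | 29% | 0.88 |

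The floor is √(1/5) = 0.447 SD, so the largest possible reduction is 1 − √(0.200/0.400) = 29%. With 40 controls the SE is √(1/5 + 1/40) = 0.474 SD, as precise as 2/(1/5 + 1/40) = 8.9 women per group. A Welch interval narrows less, from 1.46 to about 1.22 SD at 20 to 100 controls, because the five device women govern its degrees of freedom.

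**Step 3: chance signals.** Simulation with log-normal opioid use, no device effect and 200,000 replicates. The entries are the chance that the device group looks at least 30% lower; the CVs are assumptions.

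| CV | Ratio of means, 5 v 5 | Ratio of means, 5 v 40 | Ratio of medians, 5 v 5 | Ratio of medians, 5 v 40 |
|---|---|---|---|---|
| 0.5 | 12.6% | 7.5% | 15.8% | 9.2% |
| 0.8 | 22.9% | 20.0% | 25.2% | 18.7% |
| 1.0 | 27.0% | 26.3% | 28.6% | 22.7% |
| 1.2 | 29.7% | 31.2% | 30.8% | 25.3% |

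For means the gain fades as the CV rises and reverses at CV 1.2. With skewed data and unequal groups the median of the ratio of means drops below 1 (0.92 at CV 1.0), which favors the device. For medians the chance falls at every CV tried.

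**The case against.** The strongest reply is that this is a five-woman feasibility pilot. Aim 2 only looks at a trend, no analysis is planned, and acceptability, not this contrast, is the stated condition for the grant request. Five device women leave the comparison imprecise whatever the number of controls, so five against five is a defensible descriptive display, and the efficacy wording could simply be softened. This stands as an argument on priority. It does not supply a reason for stopping at five charts, and it does not reconcile the sections.

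Three stronger readings are tempting, and the documents do not support them.

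- *Every January 2019 elective cesarean is available for the taking.* The protocol does not say so, gives no pool size, and does not say IRB cover would extend to further charts. It describes pain scores and opioid use as standard-of-care data, which makes chart retrieval plausible during the hospital stay. Collection runs to 120 hours and some women go home wearing the device, so later scores may not exist for controls.
- *With five controls no like-with-like comparison is possible.* Five consecutive women who meet the participants' criteria could be taken. The comparability defects are that eligibility is not stated for controls and elective status appears only in Study Design. More charts alone cure neither. Nor do they cure self-selection: participants consent to a device offered for pain control, in a population the protocol itself describes as motivated to avoid opioids.
- *More controls always reduce chance findings.* For a ratio of means this depends on the CV and the threshold: at CV 1.0 the chance of a 20% lower mean rises from 35.1% to 37.3%.

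**Conclusion.** The point holds as a cheap improvement of modest priority. The protocol fixes five controls in Aim 2 and the endpoint sentence without a reason, gives no number in Study Design and the efficacy statement, and uses the elective restriction in only one of these places.

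Under equal SDs, half of the variance of the difference comes from the controls. A reader might infer that this half could be removed altogether, but a finite pool does not do that: the variance falls by 37.5% at 20 controls (0.400 to 0.250 SD²) and by 45% at 50 (0.400 to 0.220 SD²). The SE falls from 0.632 SD to 0.500–0.458 SD over the assumed range. The conclusion rests on equal SDs, an assumed pool of 20 to 100, and records that can be retrieved. Whatever the number of controls, the comparison cannot carry an efficacy claim.

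**What to change.** 1. Give the reference group one definition in Aim 2, both copies of the endpoint sentence, Study Design and the efficacy statement: all January 2019 elective cesareans at the hospital that meet the participants' inclusion and exclusion criteria as far as the charts show, subject to IRB approval. If a smaller number is kept, state it and the reason.
2. Abstract for controls the same demographics and medical history as for participants.
3. Report each device woman's opioid total and pain scores against the control median and quartiles, rather than relying on a ratio of means. Show results by first or repeat cesarean and by anesthesia type only if those items are abstracted for both groups; the protocol does not list them as collected.
4. State how many controls have pain scores at each time point, and note that scores after discharge may be missing.
5. Say in the report that a larger reference does not remove selection by consent.

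The cost is staff hours for chart abstraction and any IRB step needed to cover the additional records. No further device, enrolment or patient contact is involved.

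### The exclusion of daily opioid users depends on the reason for use and is not stated for the controls, so one such woman in either group could distort the five-versus-five opioid comparison

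*Protocol*

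**What the plan says.** **Device group.** Under Recruitment in the protocol, women are approached when they arrive for "elective Cesarean Section surgery". Inclusion requires only age over 18 and an elective cesarean. Of the six exclusion criteria, two bear on opioids: "Severe chronic pain condition that requires daily preoperative opioid dependence" and "Active alcoholism or drug abuse". The other four (psychological history, hemophilia, pacemaker, psoriasis) do not.

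**Control group.** Specific Aims, item 2, is to "Look at the trend of opioid consumption and pain in five post- Cesarean section women wearing device, compared to five historical consecutive controls". Study Design describes the controls as "historical controls who have had elective C-Sections in the period of January, 2019". Neither place says that the inclusion and exclusion criteria apply to them.

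**Outcome.** Data Collection and Outcome Measures collects total opioid consumption at intervals up to 120 hours and uses a standard table to "convert the oral and IV narcotic utilized by the patients to IV morphine equivalent doses (MED) for analysis purposes". No preoperative dose is named for subtraction or adjustment. The end of Pre-and-Post Metric Evaluation says that efficacy will be measured by comparing total perioperative opioid consumption between the five participants and the historical controls. The primary end point is different: the frequency of excellent tolerability together with a pain decrease of at least 20%. The protocol also says that no statistical analysis will be done.

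**The concern.** A woman who already takes opioids every day brings a dose into the postoperative total that has nothing to do with the cesarean or the device. The protocol evidently means to keep such women out, but it does so by the reason for use and not by the use itself. A woman on prescribed maintenance treatment, or on daily opioids for pain that is not both severe and chronic, meets neither opioid-related exclusion if there is no active abuse.

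The control side is more open still. Consecutive elective cesareans with no stated exclusions can include any daily opioid user, even one whom the criteria would bar from the device group. So the two groups are not selected by the same rule on a factor that acts directly on the outcome, and the looser rule is on the side where an extra opioid user makes the device look better.

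At stake is the one comparison that the protocol calls its measure of efficacy. The pilot is meant to support a later funding proposal on devices that reduce opioid use, so readers will look at this comparison even though no test is planned.

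**Working it through.** The protocol gives no planning figure to reproduce: no dose, standard deviation, effect size, alpha or power. The check is therefore how much one woman can move a group of five.

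**Inputs from the protocol.** Five women per group; total oral and IV opioid as the measure; no stated baseline adjustment.

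**Inputs assumed.** The ratio k of one daily opioid user's total to a typical woman's total (set to 1), and the prevalence p of such women among those otherwise eligible. The protocol gives neither, so ranges are shown.

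**1. Shift of the mean and share of the total.** With four women at 1 and one at k, the mean is (4 + k)/5 and her share of the group total is k/(4 + k).

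| k | Mean of five | Rise | Her share |
|---|---|---|---|
| 1 | 1.0 | 0% | 20% |
| 1.5 | 1.1 | 10% | 27% |
| 2 | 1.2 | 20% | 33% |
| 3 | 1.4 | 40% | 43% |
| 4 | 1.6 | 60% | 50% |
| 5 | 1.8 | 80% | 56% |
| 10 | 2.8 | 180% | 71% |

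She holds half the group total only from k = 4.

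**2. She is in the device group.** Suppose the device lowers use in the other four by a proportion r, and the controls average 1. The device mean is (4(1 − r) + k)/5. Setting this to 1 gives k = 1 + 4r. A true reduction of 20%, 30% or 50% in the other four is cancelled at k = 1.8, 2.2 or 3.0.

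**3. She is in the control group.** Suppose the device does nothing and the device mean is 1. The control mean is (4 + k)/5, so the apparent reduction is 1 − 5/(4 + k). At k = 2 this is 1 − 1/1.2 = 17%; at k = 3 it is 1 − 1/1.4 = 29%.

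**4. How likely she is.** The chance of at least one such woman in a group of five is 1 − (1 − p)^5. For p = 0.5%, 1%, 2% and 5% it is 2.5%, 4.9%, 9.6% and 22.6%. Because the control group admits a wider set of opioid users, the relevant p may be higher there.

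**5. An example in milligrams, also assumed.** If typical use is 80 mg IV morphine equivalents over 120 hours and her regular opioid adds 100 mg, her total is 180 mg. The group total is 4 × 80 + 180 = 500 mg, the mean is 100 mg (1.25 times typical), and her share is 180/500 = 36%.

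**The case against.** The strongest reply is that this is a five-woman feasibility pilot. The primary end point is not opioid use, no statistical analysis is planned, and Aim 2 only looks at a trend. With five women per group every value can be read directly, a median would move little, and medical history is collected from each participant, so a daily opioid user in the device group could be recognised. The document fixes no summary statistic and does not say whether a continued prior prescription counts as consumption; an analysis plan that is not shown might settle both. All doses and prevalences above are assumptions, and at a prevalence of 0.5% to 1% a group of five would have no such woman about 95% to 98% of the time.

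Most of this stands and limits the size of the point. It does not remove it. Eligibility and control selection belong in the protocol. Medical history is described for participants, not for controls. And recognising such a woman afterwards leaves the choice of what to do with her value until the data have been seen.

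Three stronger readings are not supported:

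- A reader might infer that the gap contradicts a stated opioid-naïve target population. It does not. Pre-and-Post Metric Evaluation says the device may "significantly increase patient satisfaction in individuals who are opioid naïve or adverse to taking opioids", which names women expected to benefit. It is not an eligibility requirement.
- A reader might infer that one such woman would dominate the comparison or decide its direction. That depends on a dose ratio the protocol does not give and on use of a mean or total; in the milligram example above she holds 36%.
- Project Aims/Goals says "The indication for the NSS-2 BRIDGE is for the treatment of clinical symptoms related to opioid consumption and opioid withdrawal", and a reader might infer that a daily opioid user's response would reflect that indication and not post-cesarean analgesia. The same section says the indicated symptoms also occur after cesarean, so the overlap is not peculiar to her.

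**Conclusion.** The point holds as a gap in selection with a possible, not certain, effect. On the protocol's wording, a woman on prescribed daily opioids for a reason other than severe chronic pain, without active abuse, is eligible for the device group, and any daily opioid user can be a control. Nothing elsewhere in the protocol closes either route.

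If a mean is used and one woman's total is 2 to 3 times typical, her group's mean rises by 20% to 40%. That is enough to hide a true reduction of 25% to 50% in the other four device women (r = (k − 1)/4), or to create an apparent reduction of 17% to 29% if she is a control. These sizes rest on the assumed ratio, on a mean or total as the summary, and on her regular doses being counted as consumption. The comparison affected is descriptive and secondary, although the protocol calls it the measure of efficacy. The control route matters at least as much as the wording of the criterion. The change is worth making because it is cheap and removes a known source of bias.

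**What to change.** 1. Reword the opioid criterion so that it rests on daily preoperative opioid use whatever the indication, within a period before surgery that the sponsor defines. Check it from the medical history already collected on the day of the cesarean, before the device is applied. Keep the active abuse criterion as it is.
2. State that the controls are the first five consecutive January 2019 elective cesareans whose charts meet the same inclusion and exclusion criteria, as far as charts allow. Record how many charts were passed over and why, and which criteria could not be judged from the chart.

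The cost is two edited sentences and a short chart-screening log. A few otherwise eligible women will not be enrolled and a few charts will be skipped, which matters little with a target of five per group. Results would then not describe women who take opioids daily.
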